5.5.2.3 Safety measures

The following safety outcome measures will be collected:

- duration of hospital admission associated with the index stroke (comprising associated acute and community inpatient stays where appropriate)
- death, and cause of death where known,
- readmissions to hospital and primary cause of readmission,

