Missing data will be excluded in the primary analysis. However, the sensitivity of the missing data on the outcomes will be assessed by carrying out multiple imputation assuming that the data is missing at random. If we have reason to believe that the data is not missing at random, then pattern mixture models will be used to assess sensitivity.

Adverse events will be recorded including falls and classified in terms of seriousness and relatedness and a between group analysis will be conducted for those related to the study and overall to examine if therapy has an impact on number of falls.

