5.11 Safety

5.11.1 Data Monitoring for harm

The intervention being evaluated is a neurorehabilitation therapy for spatial neglect arising from stroke. In view of the nature of the population, which are all expected to be inpatients at the time of consent, and at risk complications arising from stroke leading to extended hospital stay, readmission to hospital following discharge and subsequent stroke, the intervention being a low risk neurorehabilitation therapy comprising of lifting, grasping and moving rods in a coordinated manner directed by a therapist and which has no additional risk over usual care (as confirmed in a pilot study), and the trial primary, secondary and safety outcomes we do not intend to collect any additional safety endpoints.

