5.11.2 Safety reporting

Adverse events (serious and non-serious) will not be collected in this study.

This is a low-risk intervention. No specific risks, untoward incidents or adverse events related to the intervention were reported during development, testing and pilot work. Nine adverse events unrelated to the intervention were reported in the pilot including three deaths; five hospital admissions (due to new stroke event, infection, fall, progressive disease); and one participant was referred to end of life care'. The SIGHT neurorehabilitation intervention therapy is delivered to participants by trained therapists. If participants encounter issues with the materials provided, these will be reported by the therapist to the research team where they will be collated into an Incident Log. The participant has the right to decline any intervention at any time.

At the time of recruitment, all participants will be inpatients in acute or community hospitals. The occurrence of common complications arising from stroke, including: 1) clinical complications such as pneumonia, urinary tract infection, pressure damage and deep vein thrombosis; and 2) neurological complications such as malignant ischemic stroke and symptomatic haemorrhagic transformation, would not be influenced by intervention, although these complications may impact the delivery of the intervention. Reasons for an intervention session not being delivered as anticipated or stopped early will be recorded in the database. However, as stroke and complications arising from the stroke, is associated with increased risk of death, increased duration of hospital stay (acute and community settings as appropriate), and readmissions, the following safety data will be collected during the study:

- death (and cause)
- length of hospital stay (comprising of total of acute and community inpatient settings as appropriate)
- readmissions to hospital (including reason)

Reasons for withdrawal will also be used to ascertain any potential safety issues, including referral to end of life care.

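### The protocol plans a between-arm comparison of adverse events and falls, but its safety section says adverse events will not be collected, so that comparison cannot be run as written

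*Protocol*

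**What the plan says.** The analysis commitment is the last paragraph of Protocol 5.10.4.1 (Outcomes): "Adverse events will be recorded including falls and classified in terms of seriousness and relatedness and a between group analysis will be conducted", and it continues "for those related to the study and overall to examine if therapy has an impact on number of falls". This sets three requirements: falls are counted, events are graded by seriousness and by relatedness, and the arms are compared both on related events and on all events.

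The safety sections set a different policy. Section 5.11.2 (Safety reporting) says: "Adverse events (serious and non-serious) will not be collected in this study". Section 5.11.1, after describing the therapy as low risk and pointing to the outcomes already planned, adds: "we do not intend to collect any additional safety endpoints".

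The outcomes already planned are listed in 5.5.2.3 (Safety measures): "duration of hospital admission associated with the index stroke"; "death, and cause of death where known"; and "readmissions to hospital and primary cause of readmission". Section 5.11.2 repeats that list and adds: "Reasons for withdrawal will also be used to ascertain any potential safety issues, including referral to end of life care". It also provides for recording why a SIGHT session was missed or cut short, and for an incident log of problems with the therapy materials.

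The schedule in 5.6 (Figure 3) has a single row for safety outcome measures, marked at baseline, during the intervention, at T1 and at T2. It has no row for falls or adverse events.

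**The concern.** An analysis needs data that some other part of the protocol tells sites to collect. Here the statistics section relies on adverse-event and falls records, and the safety section tells sites not to make them. A site reading 5.10.4.1 would keep adverse-event records; a site reading 5.11.2 would not. If 5.11.2 is followed, the final report has to omit a pre-stated safety comparison or piece it together from incidental mentions of falls.

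Falls are not a remote possibility in this population. Section 5.11.2 itself gives a fall among the causes of hospital admission in the pilot, judged unrelated to the therapy. Falls are also the one event that 5.10.4.1 singles out as something the therapy might influence. Falls not recorded at the time cannot be reliably recovered later, so the timing of the correction matters.

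**Working it through.** No sample size, rate or significance level enters this point, so there is nothing to calculate. The check has three steps.

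**1. Are both statements current?** Yes. Section 8 (Protocol Amendments) says this is the first version, so neither sentence is superseded text.

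**2. Can any collected item supply what 5.10.4.1 needs?** That is a count of falls, and events graded by seriousness and relatedness, in both arms.

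| Item collected | Section | Arms | What it shows of a fall | Graded for seriousness or relatedness? |
|---|---|---|---|---|
| Death and cause | 5.5.2.3, 5.11.2 | Both | Only a fatal fall | No |
| Length of index stay | 5.5.2.3, 5.11.2 | Both | Nothing; a duration without a reason | No |
| Readmission and reason | 5.5.2.3, 5.11.2 | Both | Only a fall after discharge that leads to readmission | No |
| Reason for withdrawal | 5.11.2 | Both | Only a fall that ends participation, if the reason is given | No |
| Reason a SIGHT session was missed or shortened | 5.11.2 | SIGHT only | Only a fall that disrupts a session | No |
| Incident log | 5.11.2 | SIGHT only | Only if tied to the materials | No |

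No row gives a fall count. The session reasons and the log arise in one arm only, so adding falls found there to those found elsewhere would bias the comparison towards more recorded falls with SIGHT.

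**3. Which falls are missed?** Participants are inpatients at recruitment (5.11.2), and the intervention is delivered in hospital (5.1.1). A fall on the ward during the index admission cannot be a readmission. Unless it causes death, withdrawal or a disrupted SIGHT session, it leaves no trace. A fall at home between discharge and T2 that needs no admission leaves none either.

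Outside 5.10.4.1, no section provides for counting falls or for grading events by seriousness or relatedness.

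**The case against.** The strongest defence is that reduced collection is a deliberate and reasoned choice. Sections 5.11.1 and 5.11.2 argue that the therapy is low risk, that complications are expected in stroke inpatients whatever the arm, and that no related events were seen in earlier work. That argument may justify the policy in 5.11.2. It does not justify keeping an analysis that the policy makes impossible.

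One might also read the sentence in 5.10.4.1 as shorthand for the deaths and readmissions in 5.5.2.3. That reading fails: falls are named and are not in that list, and nothing in the list is graded for relatedness.

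Nor can the matter be left to a statistical analysis plan. Such a plan can define how data are analysed; it cannot supply data that the protocol says will not be collected.

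Two stronger inferences are tempting, and the documents support neither.

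- A reader might infer that the trial will yield no safety information, or could support no statement about safety. Deaths with cause, readmissions with reason and length of stay are collected in both arms of a randomised trial of 206 participants and can be compared. Withdrawal reasons add to this.
- A reader might try to size the problem by asking what event rate the pilot's absence of related events could still hide. That would measure uncertainty in earlier studies, not the effect of this contradiction. Its denominator is also unsettled: section 4.1 has 6 patients allocated to and completing c-SIGHT, whereas section 6.14 speaks of 11 stroke survivors completing the new version.

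What the data monitoring committee will review is in terms of reference that are not shown. It can be said only that falls and relatedness data would not exist for it to see if 5.11.2 is followed.

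**Conclusion.** The contradiction is real, and the analysis sentence in 5.10.4.1 is wrong as written. The comparison of falls, and of adverse events by seriousness and relatedness, cannot be run under the collection rules in 5.11.

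Its reach is limited. It affects one planned safety analysis. The primary outcome, the sample size and the comparison of deaths, readmissions and length of stay are unaffected. The conclusion assumes that sites follow 5.11.2 and that no case report form outside the protocol collects falls in both arms. If such a form exists, 5.11.2 is the section in error and the two still need reconciling. Either way the correction is cheap, and it should be made before falls go unrecorded.

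**What to change.** Reconcile 5.10.4.1 with 5.11.1 and 5.11.2, before enrolment (section 1.3 gives July 2025 for the first participant) or by prompt amendment. The choice is the sponsor's.

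**(a) If reduced collection is intended.** Replace the adverse-event sentence in 5.10.4.1 with a between-arm comparison of the outcomes in 5.5.2.3: deaths, readmissions and length of the index stay. State that falls and the relatedness of events will not be assessed. The cost is a wording change in one section, with no new data.

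**(b) If the falls comparison is intended.** Record falls with the same question in both arms at the existing T1 and T2 visits, add this to 5.5.2.3 and the schedule in 5.6, and amend 5.11 to say so. Limit the between-group analysis to falls and the 5.5.2.3 outcomes. Events related to a SIGHT session can arise in one arm only, so they do not belong in that comparison. Therapy staff should log them, and they should be reported descriptively for the SIGHT arm. The T1 and T2 assessors should not be asked about them, because the question could reveal allocation and undermine the blinding in 5.9.2. The cost is a short falls item at two visits already planned, a log kept by therapy staff, and matching edits to the sections named.

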5.10.4.2 Statistical Analysis Plan

A full statistical analysis plan will be drafted and approved by the trial's governance, .

5.10.4.5 Missing Data

Missing data will be excluded in the primary analysis. However, the sensitivity of the missing data on the outcomes will be assessed by carrying out multiple imputation assuming that the data is missing at random. If we have reason to believe that the data is not missing at random, then pattern mixture models will be used to assess sensitivity.

5.11 Safety

5.11.1 Data Monitoring for harm

The intervention being evaluated is a neurorehabilitation therapy for spatial neglect arising from stroke. In view of the nature of the population, which are all expected to be inpatients at the time of consent, and at risk complications arising from stroke leading to extended hospital stay, readmission to hospital following discharge and subsequent stroke, the intervention being a low risk neurorehabilitation therapy comprising of lifting, grasping and moving rods in a coordinated manner directed by a therapist and which has no additional risk over usual care (as confirmed in a pilot study), and the trial primary, secondary and safety outcomes we do not intend to collect any additional safety endpoints.

5.11.2 Safety reporting

Adverse events (serious and non-serious) will not be collected in this study.

This is a low-risk intervention. No specific risks, untoward incidents or adverse events related to the intervention were reported during development, testing and pilot work. Nine adverse events unrelated to the intervention were reported in the pilot including three deaths; five hospital admissions (due to new stroke event, infection, fall, progressive disease); and one participant was referred to end of life care'. The SIGHT neurorehabilitation intervention therapy is delivered to participants by trained therapists. If participants encounter issues with the materials provided, these will be reported by the therapist to the research team where they will be collated into an Incident Log. The participant has the right to decline any intervention at any time.

At the time of recruitment, all participants will be inpatients in acute or community hospitals. The occurrence of common complications arising from stroke, including: 1) clinical complications such as pneumonia, urinary tract infection, pressure damage and deep vein thrombosis; and 2) neurological complications such as malignant ischemic stroke and symptomatic haemorrhagic transformation, would not be influenced by intervention, although these complications may impact the delivery of the intervention. Reasons for an intervention session not being delivered as anticipated or stopped early will be recorded in the database. However, as stroke and complications arising from the stroke, is associated with increased risk of death, increased duration of hospital stay (acute and community settings as appropriate), and readmissions, the following safety data will be collected during the study:

- death (and cause)
- length of hospital stay (comprising of total of acute and community inpatient settings as appropriate)
- readmissions to hospital (including reason)

Reasons for withdrawal will also be used to ascertain any potential safety issues, including referral to end of life care.

5.12 Data Monitoring

5.12.1 Data Monitoring Committee

Further details of the roles and responsibilities of the Data Monitoring Committee (DMC), including membership, relationships with other committees, decision making processes, and the timing and frequency of interim analyses (and description of stopping rules and/or guidelines where applicable) are described in detail in the SIGHT DMC Terms of Reference (ToR).

5.12.2 Progression Criteria

Trial progress, including recruitment data collection and attrition rates, will be overseen by the Trial Management Group (TMG) consisting of the CI, co-applicants, NCTU staff and at least one PPI representative from the PPI Advisory Panel. Site and participant recruitment, randomisation, and intervention delivery and data collection will be monitored by NCTU and overseen by the trial team and Trial Management Group on an ongoing basis throughout the trial.

Potential mitigation(s) will be identified and implemented and may include replacing or adding additional sites to address site drop out or under-recruitment (tentative discussions with additional sites have been started) and addressing barriers or challenges to intervention delivery and/or data collection issues. Should any of the stop/go criteria fall into amber or red, progress, including mitigations implemented and planned will be discussed with, and advice sought from, the Trial Steering Committee. NIHR will also be approached to discuss feasibility to continue the trial should the stop/go criteria fall into amber or red.

STOP/GO CRITERIA				
By end of month 12 (6 months recruitment):	Green	Amber	Red	
Sites open (target 6)	6	5	3	
Patients randomised (target 206)	≥20%	≥12.5% and <20%	<12.5%	
Median % Intervention sessions completed	≥75%	≥40% and <75%	<40%	

(100% = 7 per patient)			
Primary outcome data completeness (T1)	>90%	≥80% and 90%	<80%

The wider PPI Advisory Panel will also meet every 4 months and once per year outreach drop-in sessions will be carried out in community settings to ensure views from a diverse pool of members of the public are incorporated into the trial. Trial Steering (TSC) and Data Monitoring Committees will be responsible for the provision of independent oversight of the trial. The TSC will be chaired by a clinical trialist and comprise two statisticians. There will be non-voting representation from the trial team and sponsor. The conduct of the oversight committees will follow the NCTU TSC/DMC terms of reference.

5.12.3 Quality Assurance and Control

5.12.3.1 Risk Assessment

The Quality Assurance (QA) and Quality Control (QC) considerations for the SIGHT trial are based on the standard NCTU Quality Management Policy that includes a formal Risk Assessment, and that acknowledges the risks associated with the conduct of the trial and proposals of how to mitigate them through appropriate QA and QC processes. Risks are defined in terms of their impact on: the rights and safety of participants; project concept including trial design, reliability of results and institutional risk; project management; and other considerations.

QA is defined as all the planned and systematic actions established to ensure the trial is performed and data generated, documented and/or recorded and reported in compliance with the principles of GCP and applicable regulatory requirements. QC is defined as the operational techniques and activities performed within the QA system to verify that the requirements for quality of the trial related activities are fulfilled.

5.12.3.2 Central Monitoring at NCTU

NCTU staff will review Case Report Form (CRF) data for errors and missing key data points. The trial database may also be programmed to generate reports on errors. Essential trial issues, events and outputs, including defined key data points, will be detailed in this Protocol and the SIGHT Quality Management and Monitoring Plan (QMMP).

5.12.3.3 On-site Monitoring

The frequency, type and intensity of routine and triggered on-site monitoring will be detailed in the SIGHT QMMP. The QMMP will also detail the procedures for review and sign-off of monitoring reports. In the event of a request for a trial site inspection by any regulatory authority, NCTU must be notified as soon as possible.

5.12.3.3.1 Direct access to participant records

Participating investigators must agree to allow trial related monitoring, including audits, REC review and regulatory inspections, by providing access to source data and other trial related

documentation as required. Participant consent for this must be obtained as part of the informed consent process for the trial.

5.12.3.4 Trial Oversight

Trial oversight is intended to preserve the integrity of the trial by independently verifying a variety of processes and prompting corrective action where necessary. The processes reviewed relate to participant enrolment, consent, eligibility, and allocation to trial groups; adherence to trial interventions and policies to protect participants, including reporting of harms; completeness, accuracy and timeliness of data collection; and will verify adherence to applicable policies detailed in the Compliance section of the protocol. Independent trial oversight complies with the NCTU trial oversight policy.

In multi-centre trials this oversight is considered and described both overall and for each recruiting centre by exploring the trial dataset or performing site visits as described in the SIGHT Quality Management and Monitoring Plan.

5.12.3.4.1 Trial Management Team

The Trial Management Team (TMT) will be set up to assist with developing the design, coordination and day to day operational issues in the management of the trial, including budget management. The membership, frequency of meetings, activity (including trial conduct and data review) and authority will be covered in the TMT terms of reference.

5.12.3.4.2 Trial Management Group

A Trial Management Group (TMG) will be set up to assist with developing the design, coordination and strategic management of the trial. The membership, frequency of meetings, activity (including trial conduct and data review) and authority will be covered in the TMG terms of reference.

5.12.3.4.3 Independent Trial Steering Committee

The Independent Trial Steering Committee (TSC) is the independent group responsible for oversight of the trial to safeguard the interests of trial participants. The TSC provides advice to the CI, NCTU, the funder and sponsor on all aspects of the trial through its independent Chair. The membership, frequency of meetings, activity (including trial conduct and data review) and authority will be covered in the TSC terms of reference.

5.12.3.4.4 Independent Data Monitoring Committee

The Independent Data Monitoring Committee (IDMC) is the only oversight body that has access to unblinded accumulating comparative data. The IDMC is responsible for safeguarding the interests of trial participants, monitoring the accumulating data and making recommendations to the TSC on whether the trial should continue as planned. The membership, frequency of meetings, activity (including review of trial conduct and data) and authority will be covered in the IDMC terms of reference. The IDMC will consider data in accordance with the statistical analysis plan and will advise the TSC through its Chair.

5.12.3.4.5 Trial Sponsor

The University of East Anglia (UEA) is the trial sponsor. The role of the sponsor is to take on responsibility for securing the arrangements to initiate, manage and finance the trial. The Sponsor is responsible for ensuring that the study meets the relevant standards and makes sure that arrangements are put and kept in place for management, monitoring and reporting.

The UEA has delegated some Sponsor's activities to the CI and NCTU, these are documented in the SIGHT delegation of responsibilities.

6 Ethics and Dissemination

6.1 Research Ethics and Health Research Authority Approval

Before initiation of the trial at any clinical site, the protocol, all informed consent forms and any material to be given to the prospective participant will be submitted to the relevant REC and to HRA for approval. Any subsequent amendments to these documents will be submitted for further approval.

The rights of the participant to refuse to participate in the trial without giving a reason must be respected. After the participant has entered the trial, the clinician remains free to give alternative treatment to that specified in the protocol, at any stage, if s/he feels it to be in the best interest of the participant. The reasons for doing so must be recorded. After randomisation the participant must remain within the trial for the purpose of follow up and data analysis according to the treatment option to which they have been allocated. However, the participant remains free to change their mind at any time about the protocol treatment and follow-up without giving a reason and without prejudicing their further treatment.

